6. INVESTIGATIONAL PRODUCT

Not applicable

7. NON-INVESTIGATIONAL PRODUCT

7.1 Name and description of non-investigational product(s)

All measurement devices used in this study were reviewed by the 'medische technologie' department of the LUMC and were used before in other studies in the LUMC. A statement from the 'medische technologie' can be found in the researchdossier (D4. 'Verklaring meetinstrumenten medische technologie').

Table for measurement devices of outcome variables

Name of device	Manufacturer	Model	CE conform 93/42/EEG of EU/2017/745 (Medical devices) OR 98/79/EEG of EU/2047/746 (in-vitro diagnostics)	Conform intended use as described in the instruction manual?
Multifunctional wearable	Corsano	Cardiowatch 287-2	Yes	Yes
Electronic Ecological momentary assessment tool	M-path Leuven	M-path app (*or similar platform)	-	Yes
Sleep Analyzer	Withings	Sleep Analyzer	No, conform 2014/53/EU	Yes

Table of measurement devices for baseline measurements

Name of device	Manufacturer	Model	CE conform 93/42/EEG of EU/2017/745 (Medical devices) OR 98/79/EEG of EU/2047/746 (in-vitro diagnostics)	Conform intended use as described in the instruction manual?
Bioelectrical impedance analyser	Akern	BIA ASE 101	Yes	Yes
Blood pressure device	Welch Allyn	ProBP3400 (or similar device)	Yes, conform 93-42/EEG	Yes
Dynamometer	JAMAR	Handdynamometer Hydraulic	Yes	Yes

8. METHODS

8.1 Study parameters/endpoints

8.1.1 Main study parameter/endpoint

The main outcome of this study will be insomnia severity which will be measured by the Dutch version of the ISI ranging from 0-28 (0-7: no clinically significant insomnia; 8-14: subthreshold insomnia; 15-21: moderate severity clinical insomnia; 22-28: severe clinical insomnia).(35)

8.1.2 Secondary study parameters/endpoints

Secondary and exploratory endpoints include:

Biological clock function

- Clockgene expression
- Core body temperature (°C)
 - Diurnal pattern
 - Time of lowest temperature
- Melatonin
 - Dim light melatonin onset (DLMO)

Physiological parameters

- Heart rate
 - Diurnal pattern
 - Average
 - Resting heart rate
 - Minimum/peak heart rate (5 and 95 percentile)
- Heart rate variability (HRV)
- Breathing rate
- Oxygen saturation (SpO2)

Mental health

- Subjective mood
 - Diurnal pattern of:
 - Positive affectivity
 - Negative affectivity
 - Energy
 - Fatigue
 - Cognition
- (objective) Electrodermal activity (emotional arousal and stress)

Behavioural factors

- Food intake
 - Frequency
 - Timing
- Habitual sleep (**Table 8.1**)
 - Sleep latency (min)
 - Duration (min)
 - Efficiency (%)
 - Sleep phases (%, min)
 - Awakenings at night (x, min)

- Rested feeling (subjective, 0-7)
- General satisfaction with sleep (subjective, 0-7)

Biochemistry

- Glucose metabolism*
- Inflammatory markers
- Liver function
- Kidney function
- Thyroid function
- Bone metabolism markers**
- White blood cell count

* TSH and ft4 will be examined. If we find differences in these markers, ft3 will be examined as well.

** These markers will only be investigated when we find differences one of the primary outcomes (e.g. change in sleep/insomnia or food intake).

Table 8.1. components of habitual sleep and their measurement method

	Withings sleepmat	Accelerometer	Questionnaire
Sleep latency (min)	X	X	
Duration (min)	X	X	
Efficiency (%)	X	X	
Sleep phases (%)	X		
Awakenings at night (X, min)	X	X	
Rested feeling (0-10) Subjective			X
General satisfaction (0-10) Subjective			X

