Sleep quality will be assessed by the Pittsburgh Sleep Quality Index (PSQI) which is a questionnaire with different questions on sleep quality in the past month. The questionnaire consists of 19 questions on 7 different domains of sleep problems; Subjective sleep quality, sleep latency, sleep duration, habitual sleep efficiency, sleep disturbances, use of sleep medication, and daytime dysfunction. Each of the sleep components yields a score ranging from 0 to 3, with 3 indicating the greatest dysfunction.

Sleep chronotype

Participants will fill out the MCTQ about their sleep behaviour at baseline to assess their chronotype.(42) Individuals are also asked to subjectively rate themselves as one of seven possible chronotypes ranging from extreme early (preferring to rise much earlier than others) to extreme late. This information is combined to determine the time of day at which the respondent is likely to feel most alert, placing them objectively in a chronotype category. The scale is scored electronically by the Web site at which it is available. Total scores can range from 16 to 86, with the lowest values representing extreme-late chronotypes.

Insomnia Severity Index

Participants will be asked to fill out the ISI questionnaire (Dutch version) a total of 5 times; first time before the start of the study to assess if participants are eligible for the study (sleep problem yes/no), the second time on the baseline measurement day which we will use as baseline, and finally, they will fill out the ISI questionnaire on the last day of each intervention. The ISI questionnaire consists of 7 questions and outcomes include: 'No clinically significant insomnia (0-7 points)', 'Subthreshold insomnia (8-14 points)', 'Moderate severity clinical insomnia (15-21 points)', and 'Severe clinical insomnia (22-28 points)'. According to the literature, a score of 10 points is an appropriate threshold when detecting insomnia cases in a community sample.(35) Therefore, we will include participants with a score of ≥ 10 in our study.

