8.3.2 Mental health investigations

Ecological momentary assessment

During the measurement week, participants will be asked to fill out the eEMA questionnaire in the Leuven mPath app (or a similar platform meeting European privacy standards) 5 times a day on set times. Participants will receive a pop-up on their smartphones and will have a window of 1 hour to fill in the questionnaire. During this 1-hour window, participants will get multiple reminders to fill in the questionnaire. The questionnaire consists of multiple questions that gather information on current mood/feelings divided into multiple dimensions: positive affectivity, negative affectivity, energetic arousal and cognition. A 7-point rating scale will be used to answer the questions. To minimize the burden of this repeated questionnaire, the time needed to fill out the questionnaire is minimised/limited to approximately 4 minutes.

Subjective sleep quality

As an addition to the eEMA, two questions will be added to the morning questionnaire, one about general sleep satisfaction and one about the participants rested feeling.

Emography

Objective emotional arousal and stress will continuously be measured by the Cardiowatch 287-2 (Corsano Health, The Hague, the Netherlands) through electrodermal activity (measured by EDA and GSR).

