Participants will wear the Corsano Cardiowatch 287-2 (Corsano Health, The Hague, the Netherlands) wrist band on their right wrist continuously during the study period. The wristband is multifunctional and is waterproof. Participants will wear the wrist band 24 hours a day. The HR is measured using a PPG (photoplethysmogram, i.e., optically obtained volumetric measurement) and ECG. The manufacturer supplies the algorithm for converting the PPG/ECG signals into a set of HR values. All data from the Cardiowatch is available real time and is transferred from the watch to the smartphone using a clinical trial app, developed by the provider, which allows the researcher to retrieve live vital sign data while conducting a blinded study. From the app, it will be uploaded to the output server through a HIPAA/AVG compliant cloud service.

Core body temperature

Core body temperature will be continuously measured by the Cardiowatch 287-2. This parameter will be derived through an algorithm of combined data from Heatflux sensor and PPG signal. Diurnal patterns of core body temperature as well as the time of lowest daily temperature will be derived from this data.

Breathing rate and oxygen saturation

Breaths per minute count and oxygen saturation (%SpO₂) will also be derived from the Cardiowatch 287-2. Data will continuously be measured throughout the study period.

Objective sleep quality

Objective sleep quality will be monitored with the Withings Sleep Analyzer (Withings, Issy-les-Moulineaux, France) and an accelerometer (Corsano Cardiowatch 287-2 (Corsano Health, The Hague, the Netherlands), see text below). Prior to the study, the Withings Sleep Analyzer will be installed in the participants bed. A smart phone is required to set-up the device and the devices must be connected to a Wi-Fi to be able to send data to the cloud. After set-up no link to the smartphone is required. The device must be connected to power.

Objective physical activity

To monitor objective physical activity, Raw accelerometry will be derived from the Corsano Cardiowatch 287-2 (Corsano Health, The Hague, the Netherlands) on their right wrist during the entire study period. Raw data will be collected at 32Hz and will be derived from the wristband similar to the variable heart rate monitoring and HRV.

Food capturing

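### Sleep latency is taken from two devices with no nightly record of when the participant tried to sleep, so the start of the interval has to be inferred; two clock-time items in the morning questionnaire would fix this.

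*Combined protocol and SAP*

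**What the plan says.** Table 8.1 (section 8.1.2) has three columns: mat, accelerometer and questionnaire. The latency row reads "Sleep latency (min) X X" and the efficiency row "Efficiency (%) X X"; in both, the questionnaire column is empty. Section 8.3.3 adds that "Objective sleep quality will be monitored with the Withings Sleep Analyzer (Withings, Issy-les-Moulineaux, France) and an accelerometer", the latter being the wrist-worn device. It defines neither latency nor efficiency: it gives no start point, denominator or event marker, and no rule for when the two devices disagree.

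Self-report does not supply the missing time:

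- Section 8.3.2 says that "two questions will be added to the morning questionnaire, one about general sleep satisfaction and one about the participants rested feeling". Neither item asks for a clock time.
- The momentary assessments are sent "5 times a day on set times", so a prompt does not mark a sleep attempt.
- The PSQI (section 8.3.1) is described as one "which is a questionnaire with different questions on sleep quality in the past month", so it cannot give nightly times.
- For the chronotype questionnaire, "Participants will fill out the MCTQ about their sleep behaviour at baseline to assess their chronotype".
- The only diary is for food (section 8.3.3). Saliva sampling on day 13 of each period is timed around bedtime (section 8.3.4), with no instruction to record that bedtime.
- Appendix B, the overview of study procedures, lists no sleep diary or lights-out log.

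Section 10.2 analyses latency and efficiency with paired t-tests, chiefly morning against evening exercise.

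**The concern.** Latency is an interval that starts when the person tries to fall asleep. A wrist accelerometer registers movement, and a mat under the sleeper can at most register presence in bed. Neither observes the intention to sleep. With no reported lights-out time, each device must infer the start by its own rule, and the protocol states neither rule.

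The crossover protects against an inference error that is the same in both conditions. It does not protect against one that depends on the condition. Section 5.1.1 places the exercise hour at 10:00–11:00 in one condition and 19:30–20:30 in the other, so the intervention itself rearranges the evening in one of them. It is plausible, though not shown, that people then go to bed at a different time or rest there for a different length of time before trying to sleep. Such a change would look like an effect on falling asleep. Without lights-out times, no later analysis could separate the two.

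At stake is the interpretation of one family of secondary results. The trial is unblinded (section 8.2) and its primary outcome is self-reported, so readers will look to the device-based sleep measures for corroboration.

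**Working it through.** **1. The plan's own figure.** The documents give no figure for latency or efficiency. The only related one is the ISI sample size in section 4.4: SD 5.4, difference 2.6, two-sided alpha 0.05, power 0.80. Taking 5.4 as the SD of the paired difference, the standardised difference is 2.6/5.4 = 0.481. The exact paired t calculation gives n = 36 (power 0.802), and 36/0.90 = 40. Both stated figures reproduce, and neither depends on how latency is measured.

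**2. How a start-point error enters latency.** Let L be the time from trying to sleep to sleep onset, and g the error in the inferred start, positive when the device starts too early. Then

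- observed latency = L + g;
- paired difference (evening − morning) = (L_E − L_M) + (g_E − g_M).

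If g_E = g_M, the error cancels. If not, the excess passes into the contrast one for one. For example, an assumed 15-minute difference in g gives a 15-minute latency difference with no change in falling asleep. That number is an input, not an estimate.

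**3. Two possible start points for one night (all times assumed).** In bed 22:00, lights out 22:45, asleep 23:15, up 07:00, no waking in between.

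| Start point | Latency | Efficiency |
|---|---|---|
| Lights out | 23:15 − 22:45 = 30 min | 465/495 = 93.9% |
| Bed entry | 23:15 − 22:00 = 75 min | 465/540 = 86.1% |

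Time asleep is 23:15 to 07:00 = 465 min. The denominators are 22:45 to 07:00 = 495 min and 22:00 to 07:00 = 540 min.

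**4. Sensitivity of latency against efficiency (assumed values).** 360 min asleep, 60 min awake after onset, 30 min from attempt to onset. Efficiency = 360/(360 + 60 + 30 + g).

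| g (min) | Latency (min) | Efficiency |
|---|---|---|
| −30 (clock starts at onset) | 0 | 360/420 = 85.7% |
| 0 | 30 | 360/450 = 80.0% |
| +30 | 60 | 360/480 = 75.0% |
| +60 | 90 | 360/510 = 70.6% |

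Over this range latency runs from 0 to 90 min around a value of 30, while efficiency moves by +5.7 to −9.4 percentage points. Efficiency can also be defined as time asleep over time in bed. That needs bed entry and exit only, and the moment of trying to sleep then drops out of the definition.

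**5. Would the proposed items cover the nights that are analysed?** Section 3 places endpoint measurement in the second week of each period: 3 × 7 = 21 days. Appendix B gives the same 21 days for the momentary assessments. The existing morning questionnaire therefore already covers the measurement weeks.

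**The case against.** A reader might infer something stronger: that the devices do not measure latency or efficiency at all in people with insomnia, and that the morning–evening contrast is biased. The documents do not support this, for five reasons.

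- **Definition.** The protocol never defines either quantity, so there is no stated definition for the devices to fail. What is documented is an unrecorded and unspecified start point.
- **Efficiency.** It need not use the sleep attempt at all. A mat installed in the bed could plausibly supply time in bed, although the documents do not say what it outputs.
- **Device performance.** Neither sleep algorithm is described and no validation data in insomnia are given. Section 7.1 reports that the hospital's medical technology department reviewed the devices. The 75-minute mat reading above is an assumption.
- **Bias.** The comparison is within participant, so a constant offset cancels. Bias requires the gap before trying to sleep to differ by condition, and nothing in the documents shows that it does.
- **Completeness of the record.** The participant booklet and the Appendix A schedule are not visible and could contain a bedtime log. Nor can one say that the PSQI is given at baseline only: section 8.1.3 allows baseline and/or later, and its Appendix B frequency cell is blank.

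There is also a fair objection to the remedy. Self-reported clock times in an unblinded trial make a device-based endpoint partly subjective.

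All of this stands, and it narrows the point. It does not supply the missing start time for latency. The past-month PSQI cannot do so, and the device review does not say where the latency clock starts. The worry about subjectivity is met by reporting device-only values alongside.

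**Conclusion.** The point holds as a cheap improvement in measurement, mainly for latency and most clearly for latency from the accelerometer. On the visible text, the start of the interval is never recorded. Any difference between conditions in the start-point error enters the latency contrast minute for minute; an equal error cancels.

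The size of any bias is unknown, and the 15- and 75-minute figures are illustrations with assumed times. Efficiency is affected less and needs chiefly a stated denominator. These are secondary and exploratory endpoints: the ISI analysis, the sample size of 36 (40 with dropout) and the main conclusion are untouched.

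The verdict assumes that the booklet and Appendix A hold no nightly record of lights-out. If they do, what remains is to define the two measures and name the source of the start time.

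**What to change.** 1. Add two clock-time items to the existing morning questionnaire in the measurement weeks: when the participant turned out the light to try to sleep, and when they finally got up.
2. In Table 8.1 and section 10.2, define latency as reported lights-out to device-detected sleep onset.
3. State the denominator for efficiency: either time in bed, or lights-out to rising.
4. Report the device-only values alongside as a sensitivity analysis, because self-reported times in an unblinded trial carry recall and reporting error.
5. If the items are not added, drop accelerometer latency and label mat latency as device-estimated time from bed entry to sleep.

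The cost is two short items on 21 mornings, in a questionnaire that section 8.3.2 puts at about 4 minutes, plus some recall error. No new device, visit or staff time is needed.

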8.1.3 Other study parameters

The following phenotypic characteristics will be collected at baseline and/or during the study duration:

- General questionnaire on age, sex, marital status, education, diet, alcohol use, smoking, self-rated health, current and previous disease, emotional health, and family members
- Anthropometric measurements
 - Height
 - Weight
 - Hip and waist circumference
 - Body fat composition through Bioelectrical Impedance Analysis (BIA)
- Physical performance
 - Physical activity level through Short Questionnaire to Assess Health enhancing physical activity (SQUASH)
 - Hand grip strength using a dynamometer

- Objective physical activity through accelerometry (*mg*)
- 4-meter walk test
- Cardiometabolic measurements
 - Resting systolic and diastolic blood pressure
 - Standard biochemistry profile (e.g., glucose, HD, triglycerides)
- Daily functioning
 - Katz activities for daily living (Katz-ADL)
 - Lawton Instrumental activities of daily living (IADL)
- Quality of life
 - EuroQol five dimension questionnaire (EQ-5D-3L)
 - EuroQol visual analogue scale (EQ-VAS)
- Comorbidities
 - Charlson comorbidity index (CCI)
- Frailty
 - Clinical frailty scale (CFS)
 - Geriatric 8 (G-8)
- Subjective sleep quality
 - Pittsburgh Sleep Quality Index (PSQI)
 - Sleep chronotypeMunich ChronoType Questionnaire (MCTQ)
- Medication use
- Medical history

8.2 Randomisation, blinding and treatment allocation

As this is a cross-over study, participants will undergo all three conditions. Participants will be randomised into two groups at enrolment using a computer-based statistical program. Both groups will start with sedentary period where after the first group will start with the active morning first followed by the active evening. For the second group, the order of the two activity interventions will be reversed (sedentary period- active evening- active morning). Blinding will not be possible in this study. However, we will minimise the interference of the researchers that will perform the analyses during the study by hiring a research nurse to lead the study. If necessary, the research nurse will be assisted by medical students.

8.3 Study procedures

Appendix A shows a snapshot of the study and a schematic overview of its procedures. **Appendix B** shows the frequency and estimated duration of all study procedures. The table distinguishes between active and passive procedures and in this way also indicates the burden of all procedures (passive procedure=less burdensome). For example, filling out the ecological momentary assessments is marked as active study procedures (more burdensome) while heart rate measurement is marked as a passive procedure (participants wearing the wrist-worn heart rate monitor). Intervention procedures

Sedentary behaviour

During the sedentary period, participants are asked to attain their inactive/sedentary lifestyle. This means that they have to refrain from all moderate to vigorous (social) physical activities.

Physical activity interventions

During the active morning and active evening interventions, participants are expected to exercise on the set hour of the corresponding intervention. Chapter 5.1.1 contains a full description of the interventions

8.3.1 Questionnaires

Screening questionnaire

Questionnaire containing all screening questions to assess whether an individual might be eligible for participation, will be distributed prior to the study as part of the screening.

General Questionnaire

General questionnaire on age, sex, marital status, education, diet, alcohol use, smoking, self-rated health, current and previous disease, emotional health, and family members will be distributed and filled out at baseline.

Daily functioning

Daily (physical) functioning will be assessed by two questionnaires on performing daily activities. Katz Activities of Daily Living (ADL)(36) includes activities such as bathing and feeding, while the Lawson Instrumental Activities of Daily Living (IADL)(37) questionnaire includes mainly household activities such as cooking and doing laundry.

Quality of life

The EQ-5D-3L(38), self-reported measure of functional health and well-being will be distributed and filled out. It consists of 5 questions on different domains. Additionally, participants will fill out the EQ-VAS.(38)

Comorbidities

From the medical records, we will derive the number of medications used and the comorbidities, from which we can constitute the Charlson Comorbidity Index.(39)

Frailty

Frailty will be measured by the clinical frailty scale.(40) Participants will be categorized on a scale from 1 (very fit) to 9 (terminally ill). Additionally, participants will fill in the G8(41), a short multidimensional assessment of 8 dimensions. The score ranges from 0-17 at which a score of 14 or lower suggests a full geriatric screening is necessary. Filling out the G8 takes approximately 3-5 minutes.

Medication use

At baseline, we will ask the participants to hand in a list of medications that they are currently using retrieved from their pharmacy or GP which will be checked by the research nurse together with the participant on the baseline measurement day in the research center.

Medical history

At baseline, we will ask participants to hand in a list of medical history and current medical diagnoses requested and retrieved from their GP which will be checked by the research nurse together with the participant on the baseline measurement day in the research center.

Subjective sleep quality

Sleep quality will be assessed by the Pittsburgh Sleep Quality Index (PSQI) which is a questionnaire with different questions on sleep quality in the past month. The questionnaire consists of 19 questions on 7 different domains of sleep problems; Subjective sleep quality, sleep latency, sleep duration, habitual sleep efficiency, sleep disturbances, use of sleep medication, and daytime dysfunction. Each of the sleep components yields a score ranging from 0 to 3, with 3 indicating the greatest dysfunction.

Sleep chronotype

Participants will fill out the MCTQ about their sleep behaviour at baseline to assess their chronotype.(42) Individuals are also asked to subjectively rate themselves as one of seven possible chronotypes ranging from extreme early (preferring to rise much earlier than others) to extreme late. This information is combined to determine the time of day at which the respondent is likely to feel most alert, placing them objectively in a chronotype category. The scale is scored electronically by the Web site at which it is available. Total scores can range from 16 to 86, with the lowest values representing extreme-late chronotypes.

Insomnia Severity Index

Participants will be asked to fill out the ISI questionnaire (Dutch version) a total of 5 times; first time before the start of the study to assess if participants are eligible for the study (sleep problem yes/no), the second time on the baseline measurement day which we will use as baseline, and finally, they will fill out the ISI questionnaire on the last day of each intervention. The ISI questionnaire consists of 7 questions and outcomes include: 'No clinically significant insomnia (0-7 points)', 'Subthreshold insomnia (8-14 points)', 'Moderate severity clinical insomnia (15-21 points)', and 'Severe clinical insomnia (22-28 points)'. According to the literature, a score of 10 points is an appropriate threshold when detecting insomnia cases in a community sample.(35) Therefore, we will include participants with a score of ≥ 10 in our study.

